4.2 Secondary endpoints

There are five secondary outcomes:

S1: Severe adverse event (SAE) within 28 days, defined as any of these events:

- Severe sepsis, defined as either (i) vasoactive treatment requirement or (ii) fluid bolus requirement $>20\text{mL/kg}$ or (iii) respiratory support requirement (mechanical ventilation).

- Fever with positive blood culture. For possible contaminants, at least two positive culture bottles were required. Possible contaminants include coagulase negative staphylococcus, micrococcus spp., non hemolytic streptococcus, Corynebacterium spp, Propionibacterium spp, Bacillus spp.
- Severe focal infection highly suspicious of bacterial cause, requiring antibiotic treatment (e.g. lungs, abdomen, CNS, skin)
- Death

S2: New episode of neutropenic fever within 28 days.

S3: Days alive without fever within 28 days.

S4: Mortality within 28 days.

S5: Time to bone marrow recovery (up to 3 month), defined as the time from start of treatment to first absolute neutrophil count (ANC) $\geq 0.5 \times 10^9$ cells/L.

Note: see Section 5.7 for details about the definitions of fever, neutropenia/neutropenic, **S2** and **S3**.

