4.3 Secondary objectives and estimands

For each of the secondary **binary** outcomes **S1**, **S2** and **S4**, the secondary objectives are to estimate the risks of the outcome in the two arms; as well as the risk differences. The corresponding clinical questions of interest are:

“What are the risks of [SAE / new episode of neutropenic fever / death] within 28 days after treatment started, when receiving the “short” and “long” treatment duration strategies, among children with cancer who started antibiotic treatment for high risk neutropenic fever of unknown origin, regardless of any intervention during the follow-up needed to ensure good clinical care? What is the corresponding risk [ratio / ratio / difference]?”

Accordingly, the corresponding estimands are defined as the primary estimands of Section 4.1, except for:

- the endpoint attributes, which are defined by the above items **S1**, **S2** and **S4**
- The intercurrent event “death within 28 days” does not exist for outcome **S4**. For **S1** and **S2**, it is implicitly addressed by the definition of the endpoint (as a classical competing event: in case death happens before the outcome of interest, the outcome of interest did not happen).
- Population-level summary: risk ratio for **S1** and **S2** and difference in risk for **S4** (between arms).

For each of the secondary **quantitative** outcomes **S3** and **S5**, the main secondary objectives are to estimate the medians of the outcome in the two arms; as well as their differences. The corresponding clinical questions of interest are:

“What are the median [number of day alive without fever within 28 days / time to bone marrow recovery], when receiving the “short” and “long” treatment duration strategies, among

children with cancer who started antibiotic treatment for high risk neutropenic fever of unknown origin, regardless of any intervention during the follow-up needed to ensure good clinical care? What is the corresponding risk difference?"

Accordingly, the corresponding estimands are defined as the primary estimands of Section 4.1, except for:

- the endpoint attributes, which are defined by the above items **S3** and **S5**

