- with **S5**, the intercurrent event “death within 28 days” is implicitly addressed by the definition of the endpoint as a classical competing event: in case death happens before the outcome of interest, the outcome of interest did not happen and the time to bone marrow recovery is set to infinity to define the median time (see e.g. [20, 2]).
- Population-level summary: Difference in median between arms.

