8.1 Binary secondary endpoints

Secondary outcomes **S1**, **S2** and **S4** are binary. For **S1** and **S2**, we will first compute the logarithm of the risk ratio and its confidence interval using a GEE approach [17], again to account for a potential within-patient correlation. Unlike for the primary analysis, here we will use a log-linear model. Specifically, the variance and link functions that define the GEE will be that of a binary family with a log link. Here again, we will use an independent working correlation structure, for the same reasons mentioned above. To compute the point estimate of the risk ratio and its confidence interval, we will then exponentiate the fitted log of the risk ratio and its confidence interval. We will not adjust for baseline variables in this analysis, mainly for three reasons already mentioned in Section 5.6. First, non-linear models do not directly provide marginal effect estimates [10]. Second, the baseline covariates are not expected to be substantially prognostic of the outcomes and third, because of the limited (effective) sample size. An example of R code corresponding to this analysis is provided in appendix A.2.

For outcome **S4** (mortality), we expect very few events (if any), say less than 1% (so, ≤ 2 in the dataset). Hence we will use an exact method instead of a GEE approach, as the asymptotic approximations implicitly used by a GEE approach would be very questionable. The method will not account for the within patient correlation, as we are not aware of any exact method that could do that. But, this is a relatively minor limitation when the risks are very small. Specifically, we will use an exact unconditional test using the score statistic ordering as in Nielsen et al. [19], and implemented in the `uncondExact2x2()` function of the R package `exact2x2`; see [8] for the mathematical details and Appendix A.3 for the specific R code that we will use.

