10.1.3 Cumulative incidence plots

To describe the timing of the binary secondary outcome **S1** and **S2**, we will report the cumulative incidence/risk function per arm graphically and with pointwise 95% CIs. That is, we will present the proportion of events observed before day t , for $t = 0, 1, 3, \dots, 28$, for each arm. The CIs will be computed again using GEE. A similar approach will be used for **S4**, if relevant (i.e., if several deaths are observed).

Cumulative incidence functions per arm will also be reported for the time to bone marrow recovery (**S5**). However, the method to compute them will be that accounting for interval censoring outlined in Section 8.2.

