10.2.4 Type of severe adverse events

To complement the analysis of **S1** (any severe adverse event), we will present the number and proportion of each individual component of the composite outcome **S1**, per arm. The individual component are listed in Section 4.2 to define **S1**. The type of observed severe focal infections will also be listed (e.g., lungs, abdomen, skin).

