11.2 Additional power calculations

After the decision to stop the trial early was taken, it has been anticipated that about 100 episodes would be included by the end of the trial. Below we provide the results of a standard power calculation [3, Sec. 3.2.1] for a sample size (i.e. number of episode, n) ranging from 90 to 110 (and $n=198$), assuming the same difference in means and standard deviation as for the initial sample size calculation detailed in Section 11.1 (and no dropout, as none were observed and dropouts were no longer expected).

Sample size (n)	90	95	100	105	110	198
Power	59%	62%	64%	65%	68%	90%

Further calculation suggest that, to get 90% power with a sample size of $n=100$ while assuming a standard deviation of 6.5 days, we would need to assume a difference in means of 4.3 days instead 3 days. Assuming a more modest difference in means of 3.5 days, the power is computed as 77%.

12 Changes to protocol-planned Analyses

1. Time to next chemotherapy is no longer a secondary outcome. It is no longer considered a secondary outcome of interest for two main reasons. First, it is influenced by numerous factors beyond infections, such as logistical and scheduling issues which introduces variability. Second, this outcome is essentially a proxy for the more relevant “Time to bone marrow recovery”, which already serves as a secondary outcome (**S5**) and more directly reflects patient recovery and treatment effectiveness.
2. Alterations in gut microbiome is no longer considered a secondary outcome. It is now considered as an exploratory outcome that will be analyzed later, hence this SAP does not pre-specify its analysis.
3. The initial statistical analysis plan mentioned a non-inferiority margin of 10% for the secondary outcomes analysis. This was not the results of carefully considerations and we will no longer consider this margin. It is irrelevant to non-binary secondary outcomes (**S3** and **S5**) and its clinical relevance in unclear for the analysis of binary outcomes (**S1**, **S2** and **S4**). Consequently, for the interpretation of the results, there will be no specific focus on whether the two-sided CIs contain a specific non-inferiority margin.

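### Does Section 4.3 take deaths out of S1 by calling death a competing event, when Section 4.2 lists death as an S1 component?

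*SAP*

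**What the plan says.** Section 4.2 defines the first secondary outcome as a list: "S1: Severe adverse event (SAE) within 28 days, defined as any of these events". The list holds severe sepsis, fever with positive blood culture, severe focal infection and death. S2 is a new episode of neutropenic fever and does not include death.

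Section 4.3 first states that the endpoint attributes are those given by items S1, S2 and S4. It then deals with death within 28 days. As an intercurrent event, death "does not exist for outcome" S4. For S1 and S2 together it is said to be covered by the endpoint definition, "as a classical competing event: in case death happens before the outcome of interest, the outcome of interest did not happen". For S5, time to bone marrow recovery, death "is implicitly addressed by the definition of the endpoint as a classical competing event: in case death happens before the outcome of interest", and there the SAP adds that the recovery time is set to infinity.

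Section 10.2.4 returns to S1: "we will present the number and proportion of each individual component of the composite outcome", per arm, using the components listed in Section 4.2. S1 enters the risk ratio of Section 8.1 and the plots of Section 10.1.3, where "we will report the cumulative incidence/risk function per arm graphically and with pointwise 95% CIs".

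On effect measures, the opening objective of Section 4.3 speaks of risk differences for all three binary outcomes. The clinical question, the population-level summary, Section 8.1 and Appendix A.2 give a risk ratio for S1 and S2.

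**The concern.** A competing event prevents the outcome from occurring; a component is the outcome. Section 4.3 names S1 explicitly and gives death the first role, while Section 4.2 gives it the second. Take a child who dies on day 10 with no earlier sepsis, bacteraemia or focal infection. Section 4.2 makes this an S1 event. A quick reading of Section 4.3 makes it a non-event.

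S1 is the severe-event composite, and Section 5.3 limits its reporting to an estimate with a confidence interval. A reader will therefore take the S1 risk ratio at face value. If a fatal case were coded as no event, the arm with the death would look safer than it was. The S1 cumulative incidence curve and the S1 analysis in the low-neutrophil subgroup (Section 10.1.4) would carry the same error.

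Section 4.3 also has two loose phrases on effect measures: risk differences where a ratio is planned for S1 and S2, and a risk difference in the question for S3 and S5, where the summary is a difference in medians.

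**Working it through.** **Step 1: the possible cases for S1.** Three cases cover every child.

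| Course within 28 days | S1 under Section 4.2 | Is the Section 4.3 condition (death before the outcome) met? |
|---|---|---|
| Non-fatal component, with or without later death | Event | No, the outcome came first |
| Death with no earlier component | Event (death is the component) | No, the death is the outcome |
| Neither | No event | No, there was no death |

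The condition is met in no row, so the rule recodes no child for S1. For S2 it does apply: a child who dies before a new neutropenic fever has had no S2 event.

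**Step 2: which section sets the coding.** Section 4.3 takes the endpoint from the items of Section 4.2 and says that death is dealt with through that definition. Section 10.2.4 uses the same component list. No section removes death from S1. Section 8.1 and Appendix A.2 take a binary outcome as given and have no separate step for deaths.

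**Step 3: size if the sentence were nevertheless misapplied.** Inputs: the sample size range "ranging from 90 to 110" in Section 11.2, split 1:1, and the mortality expectation of Section 8.1, "we expect very few events (if any), say less than 1" per cent, with two deaths as the SAP's upper figure.

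- Change in one arm's S1 risk per death with no earlier component: 1/45 = 2.2, 1/50 = 2.0 and 1/55 = 1.8 percentage points for 90, 100 and 110 episodes.
- Change in the risk ratio with 50 per arm, k non-fatal S1 events in each arm and d such deaths, all in one arm: from k/k = 1.0 to (k + d)/k. The SAP gives no S1 rate, so k is an assumption.

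| k | d = 1 | d = 2 |
|---|---|---|
| 2 | 1.5 | 2.0 |
| 5 | 1.2 | 1.4 |
| 10 | 1.1 | 1.2 |

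- Chance that at least one such death occurs: 1 − (1 − 0.01f)^n. Here 1% is the SAP's ceiling, f is the assumed share of deaths with no earlier component, and episodes are treated as independent. With f = 0.10 this is 8.6%, 9.5% and 10.4% for n = 90, 100 and 110; with f = 0.50 it is 36.3%, 39.4% and 42.4%.

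These are upper figures for the occurrence of such a death only. For the S1 result to be wrong, the analyst must also set aside the Section 4.2 list. Under the plan as written, the change is zero.

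**Step 4: effect measures.** For S1 and S2, four places (question, summary, Section 8.1, Appendix A.2) specify the ratio against one loose phrase. For S3 and S5, the objective and the summary in Section 4.3, Section 8.2 and Appendix A.4 all specify a difference in medians. The planned estimates are not in doubt.

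**The case for a change.** The best case for an edit is that an estimand's intercurrent-event attribute should name the right strategy, and for S1 it does not. The authors had a phrase for the situation, since they say that death is no intercurrent event for S4, yet they left S1 out of it and paired it with S2. They use the same competing-event wording for S5, where it does mean that the outcome never occurs. The trial is open label and recruitment has ended, so the handling of a fatal case should not depend on interpretation once the case is known. The edit would cost one sentence.

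Part of this stands. The competing-event label is wrong for S1, and S1 should not share the sentence with S2. The rest does not carry through. For S5 the SAP adds an operating rule, the infinite time. For S1 it adds none and points back to a definition that contains death. Nor is any discretion left for later: the Section 4.2 list is explicit and sits in the signed plan. A death would also appear in S4 and in the component table, so a miscoded case would show up against two other planned outputs.

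**Conclusion.** The concern identifies a clerical slip, and no change to the plan follows. The competing-event label does not suit S1, but its condition cannot be met there, and Section 4.2 already makes any death within 28 days an S1 event. No child is recoded, and no estimate, interval, plot or line of code changes. The shift of 1.8 to 2.2 percentage points per death arises only if a child dies with no earlier component and the analyst also disregards the Section 4.2 list.

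This conclusion rests on the S1 variable being built from the Section 4.2 list, which Sections 4.3 and 10.2.4 both call for. The effect-measure phrases are editorial for the same reason: every operative passage gives the risk ratio for S1 and S2, the risk difference for S4 and the difference in medians for S3 and S5.

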4.4 Exploratory outcomes

Exploratory outcomes are:

E1: Mortality within 3 months.

E2: New initiation of antibiotic treatment within 28 days, defined as antibiotic treatment restarted after at least 12 hours of stopping.

Remark: outcome **E2** can be thought as a composite outcome with “new episode of neutropenic fever” (**S2**) being one component, as a neutropenic fever systematically triggers initiation of antibiotics.

5 General Considerations

5.1 Intention-to-treat analyses

The main analyses supporting the primary and secondary objectives will use the “All episodes analysis set” that consists of all randomized episodes and correspond to Intention-To-Treat (ITT) analyses.

The ITT principle/analysis/estimand is often recommended to alleviate concerns about baseline confounding when analyzing the data. However, one drawback of the ITT estimand is that its magnitude depends on the degree to which participants receive the assigned interventions. See e.g., [6, 12]. In this trial, we expect that this is a minor issue, as good adherence is expected. Adherence data will be reported, see Section 10.2.3.

No Per Protocol analyses/estimands are pre-specified in this SAP, because non-adherence is expected to be negligible. However, post hoc analyses might be performed, e.g., if adherence data are not as good as anticipated. If performed, post hoc Per Protocol analyses are expected to be based on the “Per protocol analysis set” listed in Section 6.

5.2 Statistical Hypotheses

The null hypothesis to be tested in relation to the primary estimand (detailed in Sec. 4.1) is as follows:

- **Null hypothesis:** the mean number of days alive without antibiotic treatment within 28 days after treatment started is **the same** when the children receive the “short” and “long” treatment duration strategies¹. Formally, $\mathcal{H}_0 : \mu_1 = \mu_0$, where μ_1 and μ_0 are the mean number of days when the children receive “short” and “long” treatment duration strategies, respectively.

versus

- **Alternative hypothesis:** the mean number of days alive without antibiotic treatment within 28 days after treatment started is **different** when the children receive the “short” and “long” treatment duration strategies¹. Formally, $\mathcal{H}_1 : \mu_1 \neq \mu_0$.

We will use a two-sided test at 5% and matching 95% two-sided confidence interval (CI).

5.3 Multiplicity Adjustment

No multiple testing correction will be used, as formal hypothesis testing will be performed only for the primary estimands described in Section 4.1. Reporting for other endpoints/estimands will be limited to point estimates of effects with 95% (two-sided) confidence intervals. The widths of the intervals will not be adjusted for multiplicity and therefore it will not be possible to use them in place of formal hypothesis testing. This is in line with common recommendations [18].

5.4 Missing and interval censored data

No missing data are expected for the primary, secondary or exploratory outcomes. The patients are all children cancer patients that are monitored very closely, hence preventing missing outcome data. Missing data are not expected either for the baseline variables adjusted for in the primary analysis. In case missing data occur, this will be transparently reported as well as any change to the prespecified statistical analyses that they might cause.

Data on neutrophil counts, which are pivotal to define **S5** (time to bone marrow recovery), were not collected every day for all children. In accordance with the protocol, there were sometimes two or three days between consecutive blood samples, leading to interval censored data for some children. For instance, interval censoring [7, Sec. 16] can happen if a child is observed without bone marrow recovery a Friday (i.e., with neutrophil count $< 0.5 \times 10^9$ cells/L) and come back for the next blood sample only on Monday, when bone marrow recovery is observed (i.e., neutrophil count $\geq 0.5 \times 10^9$ cells/L). In that case, we only know that bone marrow recovery occurred between Friday and Monday. Hence, specific methods for interval censored data will be used to analyse outcome **S5** (see Section 8.2)

¹among children with cancer who started antibiotic treatment for high risk neutropenic fever of unknown origin, regardless of any intervention during the follow-up needed to ensure good clinical care.

5.5 Within-patient correlation between episodes

A child can be randomized more than once and consequently a child can contribute with more than one episode. Bone marrow recovery and subsequent chemotherapy treatment must have taken place before a new randomization of the same child can occur, as detailed in the protocol. We cannot rule out that the outcome from two episodes from the same patient are more likely similar than the outcome of two episodes from two different patients. That is, we cannot rule out within-patient correlation between episodes. To analyze the data accordingly, we will use Generalized Estimating Equations (GEE) [17] as implemented in the popular geepack package of R [13]. Standard errors will be computed via either a standard “sandwich” approach, as implemented in geepack, or non-parametric cluster bootstrap [4, Sec. 3.8] (see Sections 7 and 8).

5.6 Covariate adjustment

All estimands considered in this SAP are “unconditional treatment effect” [10]. To follow usual guidelines and to attempt to gain power [10], we will adjust for a few baseline covariates in the analysis of the primary outcome. As a linear model without interaction will be used, no standardization step will be used, since “unconditional” and “conditional” effects are the same in that case [10]. As this would not be the case for the analysis of the secondary (binary) outcomes and also because of the limited sample size and limited prognostic value of the baseline variables for the secondary outcomes, the analysis of the secondary outcomes will not use covariate adjustment. Although parametric modeling assumptions will be made for covariate adjustment, randomization provides important robustness properties to type-I error control [26].

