A.4	R code for secondary quantitative outcome S3	24

1 Statistical analysis plan approval signature page

Person writing the SAP:

Name: [name]

Position/Title: Associate Professor in Biostatistics

[figure not shown]
January 13, 2025

Signature & Date

Approved by:

Name: [name]

Position/Title: MD PhD, Senior Consultant

January 15, 2025

Signature & Date

Name: [name]

Position/Title: MD, PhD, Associate Professor, Senior Consultant

15-01-2025

Signature & Date

2 List of Abbreviations

- ALL: Acute Lymphoblastic Leukemia
- AML: Acute Myeloid Leukemia
- ANC: Absolute Neutrophil Count
- ANCOVA: Analysis of covariance
- CI: Confidence Interval
- GEE: Generalized Estimating Equations
- ITT: Intention-To-Treat
- SAE: Severe adverse event
- SAP: Statistical Analysis Plan

3 Introduction

This document is the statistical analysis plan (SAP) for an open label, investigator-initiated, parallel group, 1:1 randomized, multicenter, clinical trial of “short” versus “standard” (i.e., “long”) empirical antibiotics treatment duration of febrile neutropenia in high-risk children with cancer. Included children have an absolute neutrophil count (ANC) $< 0.5 \times 10^9$ cells/L and an expected duration of neutropenia of more than seven days. The primary endpoint is the number of days without antibiotic treatment within the first 28 days after treatment initiation. It is hypothesized that a “short” empirical antibiotics treatment duration is sufficient to prevent reinfection that would require additional antibiotic treatment days, hence superior to “standard” treatment duration. Randomization was stratified by site, via block randomization with random block size. Patient accrual has stopped early because of lower accrual rate than anticipated, as detailed in Sec. 3.1.

This SAP has been written after this decision to stop the trial early was taken. The changes to the protocol-planned analyses are summarized in Section 12. We do not consider them as major changes and the rationale for each of them is provided.

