11.1 Sample size determination

For the number of episodes to include in the trial, the initial sample size calculation was performed as followed. A mean number of 16 empirical antibiotic therapy free days was expected in the experimental group, versus 13 days in the control group. A standard deviation of 6.5 days in each arm was expected. These expected values were, among other things, based on previous results from a similar study in adult patients [1]. Standard sample size calculation for 1:1 randomization [3, Sec. 3.2.1] suggested that

$$n/2 = \frac{2 \times 6.5^2 \times (1.96 + 1.282)^2}{(16 - 13)^2} \approx 99$$

in each group, hence $n = 198$ in total, would be sufficient to obtain 90% power to show a significant difference in mean between the two arms, while controlling the type-I error at 5% (using a usual two-sided test). Accounting for up to 10% of drop-outs, the sample size was increased to $n = 198/(1 - 0.1) = 220$.

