4. The initial statistical analysis plan mentioned a different set of baseline covariates to adjust for in the analysis of the primary outcome. This was not the results of very careful considerations, but first thoughts to mimic what has been done in a similar study [1]. New careful thinking and discussions led to the conclusion that the covariates listed in Section 7 are more relevant. Of note, adjusting on thrombocyte was thought relevant based on, among other things, results from [15]. Adjusting for site was also thought relevant, as randomization was stratified by site. The decision to update the list of covariates was not based on any preliminary analysis of the outcome, as usually recommended [5].
5. Exploratory outcomes (**E1** and **E2**) and other analyses, such as the rate analyses (Section 10.1.1), have been added.

References

- [3] Chow, S.-C., Shao, J., Wang, H., and Lokhnygina, Y. (2008). *Sample size calculations in clinical research, Second Edition*. CRC press.
- [4] Davison, A. C. and Hinkley, D. V. (1997). *Bootstrap methods and their application*. Number 1. Cambridge university press.

- [5] EMA/CHMP (2015). Guideline on adjustment for baseline covariates in clinical trials. Technical report, https://www.ema.europa.eu/en/documents/scientific-guideline/guideline-adjustment-baseline-covariates-clinical-trials_en.pdf.
- [6] Evans, S. and Ting, N. (2015). *Fundamental concepts for new clinical trialists*. CRC Press.
- [7] Fay, M. P. and Brittain, E. H. (2022). *Statistical Hypothesis Testing in Context*. Cambridge University Press.
- [8] Fay, M. P. and Hunsberger, S. A. (2021). Practical valid inferences for the two-sample binomial problem. *Statistics Surveys*, 15:72–110.

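### One of the three reasons for leaving site out of the S1, S2 and E2 risk ratios does not hold for a log-link model; the cost is a modestly conservative CI if site is prognostic

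*SAP*

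**What the plan says.** Section 4.3 makes the risk ratio the summary measure for S1 and S2. Section 8.1 and Appendix A.2 estimate it by GEE with a binomial family, log link, independence working correlation and treatment as the only regressor. Section 9 analyses E2 in the same way as S2.

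Three reasons are given for not adjusting. Section 5.6 first observes that the two kinds of effect agree in a linear model without interaction, and goes on: "As this would not be the case for the analysis of the secondary (binary) outcomes and also because of the limited sample size". The same sentence adds limited prognostic value of the baseline variables. Section 8.1 lists the reasons in order. It opens with "First, non-linear models do not directly provide marginal effect estimates [10", citing regulatory guidance, followed by weak prognostic value and limited effective sample size.

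On the design, Section 3 states: "Randomization was stratified by site, via block randomization with random block size". Section 12, item 4, explains the covariates of the primary model: "Adjusting for site was also thought relevant, as randomization was stratified by site".

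**The concern.** The equality of conditional and marginal effects that Section 5.6 uses to justify adjusting the primary model also holds for the risk ratio in the log-link model planned for S1 and S2, as long as there is no interaction. It fails for an odds ratio from a logit link, which the SAP does not use for these outcomes. So one of the three reasons does not apply to the model it is meant to support.

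The consequence concerns site. The reason in Section 12 for including it comes from the design and does not depend on the outcome, so it applies to S1, S2 and E2 as well. Blocking within site removes between-site variation from the arm contrast, but an analysis without site still counts that variation in its SE. Section 5.3 limits these outcomes to estimates with confidence intervals, and Section 12, item 3, drops the non-inferiority margin. The interval is therefore the whole inferential output, from about 100 episodes where 220 were planned.

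**Working it through.** **Plan's own figures.** None is given for S1, S2 or E2: no event rate, site share or interval width. The primary sample size reproduces: 2 × 6.5² × (1.96 + 1.282)² / 3² = 98.7, so 99 per arm, 198 in all, and 198/0.9 = 220. The Section 11.2 power table also reproduces to within one percentage point (63.6% at 100 episodes, against 64% stated). It is used here only for the anticipated 100 episodes.

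**Step 1: is the log-link effect marginal?** With risk exp(a + b·treat + c·X), the marginal ratio is E[exp(a + b + cX)] / E[exp(a + cX)] = exp(b), whatever the distribution of X. Numerically, take assumed site shares of 60/30/10% and control risks of 10/20/40%:
- A common conditional RR of 1.5 gives 0.24/0.16 = 1.50.
- A common conditional OR of 1.5 gives a marginal OR of 1.46.

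**Step 2: SE with and without site.** Assume 100 episodes, n = 50 per arm, exact 1:1 balance within site and independent episodes. Let w be the site share, p the site risk and p̄ the arm risk. Then Var(log RR) is a sum over arms of:
- without site: p̄(1 − p̄) / (n p̄²)
- with site: Σ w p(1 − p) / (n p̄²)

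The second form is the large-sample sandwich variance of a log-link model with Poisson working variance, treatment and site, under balance and a common RR.

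Worked case: shares 60/30/10%, risks 10/25/40%, RR 1, so p̄ = 0.175.
- Without site: 2 × 0.144375 / (50 × 0.030625) = 0.1886, SE 0.434.
- With site: 2 × 0.13425 / (50 × 0.030625) = 0.1753, SE 0.419.
- Ratio 0.964. Around an RR of 1 the upper 95% limit moves from exp(1.96 × 0.434) = 2.34 to exp(1.96 × 0.419) = 2.27.

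Ratio of SEs (with site / without), shares 60/30/10% or equal thirds, RR 1 or 1.3:

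| Spread of site risks | Poisson variance, site | Binomial log link, site |
|---|---|---|
| none | 1.00 | 1.00 |
| 4–10 points | 0.996–0.999 | 0.992–0.999 |
| 15–20 points | 0.978–0.990 | 0.969–0.987 |
| 30 points (10/25/40%) | 0.952–0.964 | 0.937–0.954 |
| 40 points (20/40/60%) | 0.929–0.956 | 0.876–0.926 |

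Another 30-point pattern, 20/35/50% with shares 55/30/15%, gives 0.970 with Poisson variance. That is the 3% end of the range at 30–40 points.

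**Step 3: coverage.** There were 1,500 simulated trials per setting, with robust SEs and Poisson working variance (Monte Carlo error about 0.6 points). The unadjusted 95% interval covered 96–97% and the site-adjusted one 95–96%. In the rarest setting (5/10/20%) both were higher: 98.5–98.9% against 98.2–98.4%. The empirical SD of the estimate was the same to three decimals with and without site. Adding site therefore changes the stated SE and leaves the estimate almost untouched.

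**Step 4: if the RR differs between sites.** Shares 55/30/15%, balanced arms:
- Control 15/35/60%, short 30/42/60%: marginal RR 0.381/0.2775 = 1.373. Poisson variance with site gives 1.373; binomial variance gives 1.287.
- Control 20/35/50%, short 20/42/70%: marginal RR 0.341/0.29 = 1.176. Poisson variance gives 1.176; binomial variance gives 1.220.

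With Poisson variance and balance, the score equations reduce to total events in one arm over total events in the other, so the marginal RR is recovered without a common-RR assumption. A site with no events then adds nothing. In a constructed data set with one such site, the RR and its SE were the same whether that site was kept or dropped.

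**The case against.** The strongest reply is that the SAP does not rest on non-marginality alone. It also cites weak prognostic value and limited sample size, neither of which depends on collapsibility. If site is not prognostic nothing is lost, and nothing in the SAP shows that it is. That stands. A reader might infer that site was dropped solely because of the faulty argument, and the text does not support this. Still, both remaining reasons are stated for the covariates as a group. Site alone adds two coefficients, while the primary model carries 13 covariate coefficients on the same episodes (age 3, cancer 3, ANC 2, thrombocytes 3, site 2).

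It can also be said that Section 8.1 is right about non-linear models in general, and that even a log-link coefficient departs from the marginal RR when site RRs differ. This stands for binomial variance, as Step 4 shows, and it is why the variance function has to be fixed. It does not rescue the reason as given.

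Sparse data are a fair worry. In the two lower-risk simulation settings (20% at every site; 5/10/20%), some site had no event in 8–15% of runs. In several lower-risk settings the average site-adjusted SE also fell somewhat below the empirical SD (0.436 against 0.466 for 10/25/40%, RR 1), although coverage stayed at 95% or more.

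Finally, Section 12, item 4, speaks only of the primary outcome. A reader might see a contradiction with Section 5.6. There is none: the two analyses are openly treated differently, and what is missing is a sound reason for the difference as far as site is concerned.

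**Conclusion.** The point holds in a limited form. The non-marginality reason is wrong for a risk ratio from a main-effects log-link model and should be corrected whatever the size of the effect. The two other reasons are weak against the randomization stratum alone.

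The practical loss is small. The SE of the log RR would fall by about 0–3% for site risks up to 20 points apart and by about 3–12% for 30–40 points. The upper part of that second range belongs to the binomial log link; with Poisson variance it is about 3–7%. If sites do not differ, nothing is lost. All of this rests on assumed site shares, risks and effects, independent episodes and near-exact balance within site.

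A reader might infer that the planned intervals are invalid or seriously too wide. They are valid, with simulated coverage above 95%. Any excess width depends on site being prognostic, which the SAP neither shows nor expects. No test or margin hangs on these intervals.

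**What to change.** - In Sections 5.6 and 8.1, remove the non-marginality reason for S1 and S2, or restrict it to measures such as the odds ratio. If other covariates stay out, rest that on the two remaining reasons.
- For S1, S2 and E2, pre-specify one model in Section 8.1 and Appendix A.2: log-link GEE with Poisson working variance, treatment and site, independence working correlation and sandwich SEs clustered on patient. State that a site without events contributes nothing to the estimate.
- Keep the unadjusted risk ratio as a sensitivity analysis and as the fallback when events are very few, with that threshold fixed in advance.

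The target remains the marginal risk ratio. The cost is a few sentences, one model term and a changed family argument. The downside is two extra coefficients and slightly less conservative intervals in very sparse data.
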